- Examine the relationships or lack thereof between willingness of respondents to have a 4-poster device placed on their property or in their community and geographic region, respondent household characteristics, concern for and experience with tickborne diseases, and opinions on community tick control

Hypotheses

We expect that respondent willingness to have a 4-poster device placed on their property or in their community will be related to concern for and experience with tickborne diseases, opinions on community tick control, and previous experience with 4-poster devices in the community. As with many other tickborne disease prevention measures, we hypothesize that acceptance and support for 4-poster devices as a communitywide tick control method increases with perceived risk of tickborne disease and previous infection with a tickborne disease.

Intended Use of Study Findings

We will use results of the survey to:

- Inform whether future efforts to utilize devices as a form of community tick control in high LDI counties are warranted based on willingness of respondents to have a device placed on their properties or in their communities and primary reasons for lack of willingness
- Assess the feasibility of conducting a 4-poster intervention study in high LDI counties in CT and NY to assess impacts on human-tick encounters and tickborne disease
- Identify specific communities with high levels of acceptance where a future 4-poster intervention study could potentially be conducted

Timeline

March-April 2020

- Initiate survey recruitment activities
- Enroll survey respondents
- Survey respondents complete web-based survey

May 2020-August 2020

- Data cleaned and analyzed
- Manuscript of findings prepared

STUDY DESIGN

Using a cross-sectional design, we will conduct a population-based survey among residents of high LDI counties in CT and NY from March-April of 2020. We will conduct descriptive analyses of survey results to determine respondents' acceptance of 4-poster devices as a means of community tick control, and evaluate associations, if any, between respondent willingness to have a 4-poster device placed on their properties or in their communities

and respondent and household characteristics, concern for and experience with tickborne diseases, and opinions on community tick control.

STUDY POPULATION

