We will send survey invitations to a random sample of residences in select high LDI counties in CT and NY (Appendix A). One adult over the age of 18 years from each residence will be asked to respond to the survey. Random selection of addresses will be proportional to county population in CT. In NY, random selection of addresses will be stratified to allow for comparison between Suffolk County, where 4-poster devices have been deployed in several towns since 2008, and seven high LDI Hudson Valley counties with no previous exposure to 4-poster devices in the community (the pooled populations of Westchester, Rockland, Putnam, Orange, Dutchess, Ulster, and Sullivan counties). We aim to recruit at least 1500 individuals for this study (at least 500 respondents in CT and at least 500 respondents from each of two regions in NY).

- Target population: adult residents of all eight counties in CT (all counties meet LDI criteria), residents of seven high LDI counties in Hudson Valley, NY (Westchester, Rockland, Putnam, Orange, Dutchess, Ulster, Sullivan) and one high LDI county in Long Island, NY (Suffolk)
- Sampling frame: 1500 randomly selected households (500 in CT; 1000 in NY) in all 8 counties in CT and 8 counties in NY
- Sampling unit: households
- Observation unit: an individual over the age of 18 within a household

Inclusion Criteria

Survey respondent must be adults ≥ 18 years of age.

Recruitment and Enrollment

We will randomly recruit from among all residents living at residential addresses on file with the U.S. Postal Service (USPS) in all 8 counties in CT and 8 high LDI counties in NY. USPS updates this list monthly based on change of address submissions; this list is not available directly from USPS, but addresses from this list can be purchased from marketing companies. In this case, we will use an existing purchased list of addresses from a company we have worked with for other studies, Marketing Systems Group (MSG). This company will randomly select addresses for identified high LDI counties in CT and NY. The number of addresses selected per county will be proportional to county size in CT and proportional to the pooled population of the 7 Hudson Valley counties in NY. The number of addresses selected in Suffolk County, NY will allow for comparisons to be made between responses from residents of Suffolk County to those of the 7 Hudson Valley counties (see Estimated Number of Respondents).

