With a minimum necessary sample of 500 respondents in CT and 1000 in NY and an anticipated response rate of 5% (a conservative estimate based on the response rate from a recent TickNET convenience sample survey), we will identify a random selection of 10,000 addresses in CT and 20,000 in NY (10,000 across all included Hudson Valley counties and 10,000 from Suffolk County) for recruitment, for a total of 30,000 addresses.

Once selected, per above, CT and NY EIP sites will then mail survey invitations in the form of postcards (Appendix B) to eligible respondents. This postcard will:

- explain the purpose of the study, scope of respondent involvement, and compensation for respondents' time
- define eligibility criteria
- give the respondent the link to the survey (via a typed link as well as scannable QR code) with a unique access code
- tell the respondent the survey expiration date (~4 weeks from receipt of invitation)
- ask the respondent to take the web-based survey if interested in participating
- give study website (Appendix H) and EIP site contact information in case of questions, in case the respondent would prefer to take the survey over the phone, or in case the respondent would like to

withdraw.

Duration of Respondent Involvement

In this study, respondents will complete one web-based survey (Appendix D), which may be taken over the phone with an EIP site study coordinator if so desired by the respondent. The survey will take 10 minutes or less to complete. The surveys will expire roughly four weeks from the time respondents receive the survey invitations or after reaching a maximum of 2000 respondents. Potential respondents will receive an additional postcard (Appendix C) reminding them to take the survey two weeks after the initial postcard.

After completion of the survey, respondents will be mailed a thank you letter (Appendix F) with a \$10 gift card.

Estimated Number of Respondents

This study will require a sample size of 500 respondents in CT and 1000 in NY for a total of 1500 respondents.

Our sample size calculation is based on the following inputs:

- Expected response of 50% of respondents likely to support placement of a 4-poster device on their own property (this is a conservative estimate, as acceptability of 4-poster devices has not previously been assessed)
- 95% CI
- Acceptable error rate of +/- 5%
- Stratification by state to allow for comparisons to be made between CT and NY

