- Additional demographics (gender of the person about whom information will be collected, whether they rent or own their property, approximate property size, number of household members, whether any of the household members are children under the age of 18)
- Whether the address the postcard was sent to is the respondent's mailing address and if not, what the correct mailing address is for the respondent

DATA ANALYSIS PLAN and SUMMARY

Descriptive analyses of survey responses will be conducted to describe the proportion of respondents who would support placement of a 4-poster device on their property, on other private lands in their neighborhood, and on public lands in their community, and primary reasons for not supporting device placement in these locations. Additionally, respondent and household characteristics, concern for and experience with tickborne diseases, and opinions on community tick control will be described. Analytic statistical methods will be used to evaluate the association (if any) between respondent willingness to have a 4-poster device placed on their property or in their community and respondent and household characteristics, concern for and experience with tickborne diseases, opinions on community tick control, and potential for device placement on property based on ownership of property, property size, and residence in an area classified as suburban or rural. In NY, we will compare responses to all questions between Suffolk County (where 4-poster devices have previously been used for tick control) and the 7 Hudson Valley counties. Lastly, we will evaluate any differences in this association by state.

DATA MANAGEMENT PLAN

Information Management and Analysis Software

For this study, REDCap, Microsoft Access, Microsoft Excel, and R will be used for data entry, management, and analysis.

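### Equal strata and no stated weighting mean that a pooled New York proportion, and any overall one, need not estimate acceptance among the target adult residents

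*Protocol*

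**What the plan says.** Under STUDY DESIGN the protocol says that "we will conduct a population-based survey among residents of high LDI counties in CT and NY". Under STUDY POPULATION the target is given as "Target population: adult residents of all eight counties in CT", together with residents of seven Hudson Valley counties and of Suffolk County.

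The recruitment goal is "at least 500 respondents in CT and at least 500 respondents from each of two regions in NY". Recruitment and Enrollment assumes "an anticipated response rate of 5" per cent and therefore mails 10,000 addresses in Connecticut and, in New York, "10,000 across all included Hudson Valley counties and 10,000 from Suffolk County". Stratum population plays no part in these numbers. Within regions, addresses are drawn "proportional to county size in CT and proportional to the pooled population of the 7 Hudson Valley counties in NY". One adult per residence is asked to answer.

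Estimated Number of Respondents plans a comparison between Connecticut and New York, and one between Suffolk and the Hudson Valley. DATA ANALYSIS PLAN and SUMMARY will "describe the proportion of respondents who would support placement of a 4-poster device on their property", and likewise for neighbourhood and public land. Nowhere does the protocol mention design weights, post-stratification or non-response adjustment.

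**The concern.** A stratified sample with equal numbers per stratum suits a comparison of strata. A proportion pooled across those strata does not describe the population unless the strata are put back to their population shares, have equal populations, or have equal acceptance.

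The protocol gives reason to doubt equal acceptance. Under Hypotheses it expects willingness to depend on earlier community experience with the devices, and it separates Suffolk from the Hudson Valley on exactly that ground. Allocation therefore ignores population along the axis where a difference is predicted.

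Acceptance is the primary objective. It is meant to inform whether device programmes are warranted and whether a later intervention study is feasible. A distortion from the mix of strata does not appear in a confidence interval, and it carries over in full to the difference between Connecticut and New York.

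**Working it through.** **The plan's own figures.** With 50% expected acceptance, 95% confidence and a margin of 5 points, n = 1.96² × 0.25 / 0.05² = 384.1, so 385 per stratum. The plan states 500, which is more than its inputs require; this is a separate matter and on the safe side. The mailing numbers reproduce: 500 / 0.05 = 10,000 per stratum and 1,500 / 0.05 = 30,000 in all.

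**Half-widths without weighting,** 1.96 × 0.5 / √n: 4.4 points at 500, 3.1 at 1,000, 2.5 at 1,500. For Connecticut (500) minus New York (1,000): 1.96 × √(0.25/500 + 0.25/1,000) = 5.4 points.

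**Assumed inputs.** The documents give no stratum populations. Shares for Connecticut / Hudson Valley / Suffolk are taken from 0.40 / 0.35 / 0.25 to 0.60 / 0.30 / 0.10. Suffolk's share s of the New York target is then 0.25/0.60 = 42% down to 0.10/0.40 = 25%. The acceptance gap between Suffolk and the Hudson Valley is taken as 10 or 20 points.

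**New York figure.** With equal strata, Suffolk supplies half of the respondents, so bias = (0.5 − s) × gap.

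| Suffolk share of NY target | Gap 10 points | Gap 20 points |
|---|---|---|
| 42% (0.25/0.60) | 0.8 | 1.7 |
| 25% | 2.5 | 5.0 |

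The bias in the difference from Connecticut has the same size. For example, let acceptance be 50% in Connecticut, 50% in the Hudson Valley and 70% in Suffolk. Unweighted, New York is 60.0% and the state difference is 10.0 points. Weighted, New York is 58.3% or 55.0% and the difference is 8.3 or 5.0 points.

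**Overall figure, if one is reported.** Bias = mean of the three stratum proportions − Σ(share × proportion). At 40% / 50% / 60%, the unweighted figure is 50.0%. The weighted figure is 0.40×40 + 0.35×50 + 0.25×60 = 48.5%, or 0.60×40 + 0.30×50 + 0.10×60 = 45.0%. The bias is 1.5 to 5.0 points. With equal acceptance everywhere, both biases are zero.

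**Regional figures.** Mailing is proportional to county size and the planned response is the same 5% everywhere, so Connecticut and the Hudson Valley are self-weighting by county at address level; Suffolk is one county. Two routes to bias remain:

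- Differential response. If two equal halves of a region accept at 40% and 60% and respond at 4% and 6%, the respondents show (4×40 + 6×60)/10 = 52% against 50%. At 3% and 7% they show 54%.
- One adult per household while the target is adults. If 30% of households have one adult and 70% have two (assumed), one-adult homes hold 0.3/(0.3 + 1.4) = 17.6% of adults but supply 30% of respondents. A gap of 10 to 20 points gives 1.2 to 2.5 points.

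**Cost of weighting by stratum.** Design effect overall = 3 × Σ share²: 3 × 0.345 = 1.04 to 3 × 0.46 = 1.38, giving half-widths of 2.6 to 3.0 points. For New York, 2 × (s² + (1 − s)²) = 1.03 to 1.25, giving 3.1 to 3.5 points.

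**The case against.** The strongest reply is that the protocol never calls its proportions raw or unweighted, and that weighting is often left to a statistical analysis plan, which may exist here. Equal allocation is also deliberate: it serves the comparison of Suffolk with the Hudson Valley, and the survey is sized by stratum. Non-response and self-selection are openly discussed, and the protocol concedes that the samples will probably not generalise to each state. Every size given above rests on assumed shares and gaps.

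Much of this stands. That the figures will be unweighted is an inference from a stated measure and a silent plan. No overall proportion is expressly promised, so the New York figure is the firmer ground. The concession on generalisability concerns who is left out of the sample and does not address the mix of strata among those who are in it.

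A reader might go further and infer that the regional proportions also fail to estimate acceptance, because counties that respond faster fill the 500. The documents do not support that. The 500 is a minimum, the only cap is 2,000 respondents in total, and "Random selection of addresses will be proportional to county population in CT", with a like rule in the Hudson Valley, removes county bias if response is uniform. The county argument cannot apply to Suffolk at all.

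**Conclusion.** The concern holds for pooled figures. Computed as the protocol describes, the New York proportion used against Connecticut, and any overall proportion, need not estimate acceptance among the target adult residents. Under the assumed ranges the New York error is about 0.8 to 5 points. At the upper end this exceeds the 3.1-point half-width of the New York figure and approaches the 5.4-point half-width of the state difference. The error requires strata that differ in both population and acceptance; the second is what the protocol itself expects. It also takes Suffolk as half of New York respondents, which follows from the planned equal response and would shift if response differed.

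For the three regional proportions, bias is a risk under differential response or from taking one adult per household. It does not follow from the allocation of addresses to counties.

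**What to change.** In DATA ANALYSIS PLAN and SUMMARY:

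- Make the three regional proportions the main results.
- Give any New York or overall proportion, and the comparison of Connecticut with New York, with weights proportional to stratum population and design-based standard errors. Show the unweighted figure alongside.
- As a sensitivity analysis, weight within region for household size, tenure and county. State that this does not remove bias from interest in ticks or in the devices, which the protocol names as a likely source. The survey records the number of household members and whether any are children, so the number of adults is only approximated where children live.

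This needs a few sentences and public population counts, and no new data. Intervals for pooled figures widen by the amounts shown in the working. For the sensitivity analysis, 500 per region tolerates a design effect of 500/384.1 = 1.30 before the 5-point margin is lost. Tenure alone, with 70% owners in the population and 80% to 85% among respondents (assumed), costs 0.7²/0.8 + 0.3²/0.2 = 1.06 to 0.7²/0.85 + 0.3²/0.15 = 1.18. The joint cost of all three variables has not been worked out and should be reported with the results.

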APPENDIX MATERIALS

Appendix A: High Lyme disease Incidence Counties Used for Recruitment in Study

Appendix B: Survey Invitation Postcard

Appendix C: Survey Reminder Postcard

Appendix D: Survey

Appendix E: Video to Accompany Survey

Appendix F: Thank You Letter

Appendix G: CDC Study Website
